### ***Partial Response with Lymphocytosis (PRL)***

The overall response will be PRL when ALL of the following criteria are met:

- Lymphocyte count is stable or increased from baseline
- All other criteria for PR or better are met.

An increase in blood lymphocyte count by itself does not uniformly indicate an increased tumor burden but may reflect redistribution of leukemia cells from lymphoid tissues to the blood. In such cases, increased lymphocytosis alone is not a sign of treatment failure.

**Progressive Disease (PD)** if any of the parameters in group A or B indicate progression

- Group A:
  - Lymph node response is PD
  - Liver and spleen assessment shows PD
  - Circulating lymphocytes increase  $\geq 50\%$  from nadir (unless PRL, as above)

Elevation of treatment-related lymphocytosis, particularly during the initial phase of treatment, will not be considered PD unless at least 1 other feature shows worsening (ie, lymphadenopathy, splenomegaly, anemia or thrombocytopenia meet criteria for disease progression) at the same evaluation or the next evaluation.

- Group B:
  - Platelet count decreases  $\geq 50\%$  from baseline secondary to CLL
  - Hemoglobin decrease of  $\geq 2$  g/dL from baseline secondary to CLL
  - Marrow shows increase of CLL cells by  $\geq 50\%$  on successive biopsies

Transformation to a more aggressive histology (Richter syndrome or Richter transformation) is also considered PD. The diagnosis of Richter transformation should be established by lymph node or other tissue biopsy.

**Stable Disease (SD):** if participant parameters do not meet criteria for PR, PD or CR

**Not evaluable (NE):** if any of the imaging, constitution and blood parameters cannot be assessed and criteria for PD are not met:

Note: Missing or inconclusive bone marrow data will not drive an assessment of NE by itself.

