### Response Category Definitions

**Complete Response (CR):** All criteria from both groups have to be met.

- Group A:
  - All lymph nodes (none  $\geq 1.5$  cm)
  - Liver and spleen are normal
  - Participant should have no constitutional symptoms
  - Circulating lymphocyte count is normal ( $<4 \times 10^9/L$ )
- Group B:
  - Platelet count  $\geq 100 \times 10^9/L$
  - Hemoglobin  $\geq 11.0$  g/dL (untransfused and without erythropoietin)

- Neutrophils  $\geq 1.5 \times 10^9/\text{L}$  (without exogenous growth factors)
- Normocellular marrow with no CLL cell or B-Lymphoid nodules

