### 10.9.1.4 iwCLL Summary Table

The following table summarizes the assessments based on both imaging and hematological parameters [Hallek, M., et al 2018].

Group	Parameter	Complete Response	Partial Response	Progressive Disease	Stable Disease
A	Lymph nodes	CR (see lymph node response table)	PR (see lymph node response table)	PD (see lymph node response table)	SD (see lymph node response table)
	Liver and/or spleen size	CR (see liver and spleen response table)	PR (see liver and spleen response table)	PD (see liver and spleen response table)	SD (see liver and spleen response table)
	Constitutional symptoms	None	Any	Any	Any
	Circulating lymphocyte count	Normal	Decrease $\geq 50\%$ (from screening)	Increase $\geq 50\%$ (from nadir)	Change of -49% to +49%
B	Platelet count	$\geq 100 \times 10^9/L$	$\geq 100 \times 10^9/L$ or increase $\geq 50\%$ over screening	Decrease $\geq 50\%$ (from screening secondary to CLL)	Change of -49% to +49%
	Hemoglobin	$\geq 11.0$ g/dL (untransfused and without erythropoietin)	$\geq 11.0$ g/dL or increase $\geq 50\%$ over screening	Decrease $\geq 2$ g/dL (from screening secondary to CLL)	Increase $< 11$ g/dL or $< 50\%$ over screening or decrease $< 2$ g/dL
	Marrow	Normocellular, no CLL cells, no B-lymphoid nodules	Presence of CLL cells, or of B-lymphoid nodules or not done	Increase of CLL cells by $\geq 50\%$ on successive biopsies	No change in marrow infiltrate
	Neutrophils	$\geq 1.5 \times 10^9/L$ (no exogenous growth factors)	Non-CR (Not meeting criteria for CR)	Non-CR (Not meeting criteria for CR)	Non-CR (Not meeting criteria for CR)
Abbreviations: CLL=chronic lymphocytic leukemia; CR=complete response; PD=progressive disease; PR=partial response; SD=stable disease.					

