Extramedullary Disease by Physical Examination	
 
Spleen and/or Lymph nodes which were assessed as Enlarged at baseline are assessed as Normal/Not Enlarged or
 
No EMD is present at baseline and post-baseline
 

Radiology Overall Response	
 
Any but PD
 

New Symptomatic Disease	Absent
Minor Response	No new signs of active disease or progression
Serum IgM	MR ( $\geq 25\%$ and $< 50\%$ reduction in Serum IgM from baseline)
Extramedullary Disease by Physical Examination	
 
Spleen and/or Lymph nodes which were assessed as 'Enlarged at baseline' are assessed as 'Normal/Not Enlarged' or 'Enlarged – Reduction from baseline' or
 
No EMD is present at baseline and post-baseline
 

Radiology Overall Response	
 
Any but PD
 

New Symptomatic Disease	Absent
Stable Disease	Not meeting the criteria for CR, VGPR, PR, MR, PD, NE or NED
Progressive Disease (PD)	Any of the categories meet the criteria for progression
Serum IgM	
 
PD unconfirmed, or
 
PD confirmed if serum IgM is the only indicator of PD (<math>\geq 25\%</math> in serum IgM from nadir)
 
Absolute increase of <math>> 5</math> g/L is required when increase of IgM is the only applicable criterion
 

Extramedullary Disease by Physical Examination	
Either spleen or lymph nodes are assessed as 'Enlarged New/recurrent' or 'Enlarged- Unequivocal Progression'
 
Progression due to lymph node/spleen enlargement by PE only should be unequivocal, and cannot drive progressive disease unless supported by other data (eg, IgM meets the criteria for PD as defined above)

Radiology Overall Response	PD
Bone Marrow	Positive (New or recurrent involvement in bone marrow associated with WM)
New Symptomatic Disease	Yes
Not evaluable	NE require AT LEAST ONE of the following, and no evidence of PD
Serum IgM	
Not available/evaluable or
 
All available IgM values are confounded by plasmapheresis

Extramedullary Disease by Physical Examination	Spleen and/or Lymph nodes were assessed as Enlarged at baseline and follow-up assessments are not performed
Radiology Overall Assessment	NE

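### CLL/SLL lymphocyte progression rule has no absolute floor, so a responder far below baseline can meet PD on a move within the normal range

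*Combined protocol and SAP*

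**What the plan says.** Section 10.9.1.3 assigns progressive disease "if any of the parameters in group A or B indicate progression". The Group A lymphocyte parameter is a rise of at least 50% "from nadir (unless PRL, as above"). Two exemptions follow from that section:

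- **PRL.** Both conditions must hold: "Lymphocyte count is stable or increased from baseline" and "All other criteria for PR or better are met". Section 8.2.1.1 adds that PRL may preclude PD that rests on lymphocytosis alone.
- **Treatment-related lymphocytosis.** This "will not be considered PD unless at least 1 other feature shows worsening", at the same or the next evaluation.

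The summary table in Section 10.9.1.4 restates the PD cell as "Increase $\geq 50\%$ (from nadir") and carries neither exemption. Its stable-disease cell runs from -49% to +49%.

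For complete response, Section 10.9.1.3 requires that "Circulating lymphocyte count is normal", defined as below 4 ×10^9/L.

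Section 8.2.2.1.2 lets the investigator keep a clinically stable participant on treatment until a repeat non-imaging assessment 4 to 6 weeks later. DOR (Section 9.4.2) and PFS (Section 3) both end at progression or death, as assessed by the investigator.

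**The concern.** A purely relative threshold becomes very sensitive when the reference value is small. Once a CLL responder's count has fallen into the normal range, a change of a few tenths of a unit is a 50% rise. That change carries no evident information about the disease, yet the text makes it progression, and no precedence rule says what to do when CR and PD criteria are met together.

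The protocol guards against this elsewhere in Appendix 9. CLL target nodes must exceed 1.5 cm and grow by 0.5 or 1 cm as well as by 50% in PPD. Existing splenomegaly must grow by at least 1 cm. For WM/LPL, an absolute IgM increase of more than 5 g/L "is required when increase of IgM is the only applicable criterion". CLL platelet and hemoglobin declines must be secondary to CLL. The lymphocyte rule has neither a floor nor an attribution clause.

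At stake is the progression date. Read literally, the rule would shorten DOR and PFS in CLL participants with deep lymphocyte responses.

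**Working it through.** The plan gives no figure to reproduce; this is a check of a definition.

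**Step 1: where the two criteria overlap.** PD needs current ≥ 1.5 × nadir. The CR lymphocyte criterion needs current < 4 ×10^9/L. Both can hold when 1.5 × nadir < 4, that is, nadir < 4/1.5 = 2.67 ×10^9/L.

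**Step 2: a CLL responder.** Baseline 50, nadir 1.0, current 1.6 ×10^9/L.
- Rise from nadir: 1.6/1.0 - 1 = 60%, so the PD parameter is met.
- Normal limit: 1.6 < 4, so the CR lymphocyte criterion is met.
- PRL: change from baseline is 1.6/50 - 1 = -96.8%. The count is neither stable nor increased, so PRL fails.
- Treatment-related lymphocytosis: a count of 1.6 is normal, so this exemption does not evidently apply.

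**Step 3: a participant with a normal baseline.** Baseline 1.2, nadir 0.8, current 1.25 ×10^9/L.
- Rise from nadir: 1.25/0.8 - 1 = 56.25%, so the PD parameter is met.
- Current exceeds baseline. If all other PR criteria are met, the visit is PRL and is exempt. It is PD only if they are not met.

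**Step 4: illustration of size.** The documents give no within-person CV, so a range is assumed. The true count is constant and observed counts are lognormal with σ = √ln(1 + CV²). PD is flagged when a count is at least 1.5 times the lowest earlier count. Assessments fall at weeks 12, 24, 36 and 48, with at least 200,000 simulated participants per CV. For the high-baseline responder the nadir comes from the four post-baseline counts. For the normal-baseline participant the baseline count is included. The confirmed row requires an independent repeat sample also at or above 1.5 times the nadir.

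| At least one false PD by week 48 | CV 10% | 15% | 20% | 25% |
|---|---|---|---|---|
| High baseline, single count | 1% | 13% | 30% | 43% |
| High baseline, repeat must confirm | 0.1% | 3% | 10% | 19% |
| Normal baseline, PRL ignored | 2% | 19% | 41% | 57% |
| Normal baseline, otherwise in PR, PRL applied | <0.1% | 1% | 5% | 9% |

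Hand check at CV 20%: σ = 0.198. For one pair of visits the chance is Φ(-ln 1.5/(σ√2)) = Φ(-0.405/0.280) = Φ(-1.45) = 0.074. Four visits make six ordered pairs, so the union bound is 6 × 0.074 = 44%. The simulated 30% lies below it, as it should.

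**The case against.** **The exemptions narrow the rule considerably.** A reader might infer that every lymphocyte rise of 50% from nadir is PD. The text does not say so: PRL is exempt in the criterion itself, and treatment-related lymphocytosis is exempt in the next paragraph. A reader might also infer that SLL participants with normal counts are the most exposed, at the rates in the third row of the table. That does not hold for DOR, which exists only for responders. A normal-baseline participant otherwise in PR is largely protected by PRL, as the fourth row shows. Reading stable in the PRL definition as the table's ±49% band would protect them further. This part of the objection stands, and it confines the point mainly to responders whose counts are well below baseline.

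**The investigator can wait for a repeat.** This also stands in part. Section 8.2.2.1.2 permits confirmation, and Section 10.9.1.3 itself warns that a lymphocyte rise alone need not mean more tumor. But confirmation is discretionary and adds no floor. If investigators simply disregard such rises, the progression date rests on unwritten judgment.

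**The missing floor may be faithful to the source.** The endpoint is defined per iwCLL 2018, which was not available for this check. A reader might infer a transcription error, but the documents cannot settle that. Nor can they support a claim that every other nadir-based rule in Appendix 9 has a floor: the WM/LPL wording on the sum of products (Section 10.9.3.2.2) is ambiguous.

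**Little depends on it.** This stands. About 6 to 12 participants are planned across several histologies, and CLL is described as rare in Japan. No hypothesis is tested. DOR is summarized only if the number of responders permits, with details deferred to the sSAP. DLT-based dose decisions are not shown to be affected.

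**Conclusion.** The concern holds in a limited form. Outside PRL and treatment-related lymphocytosis, the CLL/SLL lymphocyte PD parameter has no absolute floor. A responder well below baseline can meet PD while the CR lymphocyte criterion is still met, whenever the nadir is below 2.67 ×10^9/L. The summary table makes matters worse by omitting both exemptions.

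The contradiction follows from the text alone and needs no assumption. The rates do: they rest on an assumed CV, independent lognormal variation, a constant true count and mechanical application of the rule. At a CV of 10% the problem is about 1%; at 20% or more it is material for an affected participant, even with a confirming repeat (10% at CV 20%).

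The importance is minor, because only descriptive DOR and exploratory PFS in a small CLL/SLL subset are exposed.

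**What to change.** Reconcile the CR definition, the PD definition in Section 10.9.1.3 and the table in Section 10.9.1.4. State that, for dating progression in DOR and PFS, a lymphocyte count that still meets the protocol's normal limit for CR (below 4 ×10^9/L) is not PD on lymphocytes alone. Carry the PRL and treatment-related lymphocytosis exemptions into the table's PD cell.

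The sponsor should check the wording against the named iwCLL 2018 criteria and document any departure. Because progression also bears on stopping treatment, the change should be reconciled with Sections 7.1, 8.2.2.1.1 and 8.2.2.1.2. No treatment-stopping rule is proposed here.

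The cost is a clause in the text and an edit to the table, with no new data. The downside is that a true rise starting below 4 ×10^9/L is dated as progression slightly later, when it reaches that limit or another parameter progresses.

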### 10.9.1.4 iwCLL Summary Table

The following table summarizes the assessments based on both imaging and hematological parameters [Hallek, M., et al 2018].

Group	Parameter	Complete Response	Partial Response	Progressive Disease	Stable Disease
A	Lymph nodes	CR (see lymph node response table)	PR (see lymph node response table)	PD (see lymph node response table)	SD (see lymph node response table)
	Liver and/or spleen size	CR (see liver and spleen response table)	PR (see liver and spleen response table)	PD (see liver and spleen response table)	SD (see liver and spleen response table)
	Constitutional symptoms	None	Any	Any	Any
	Circulating lymphocyte count	Normal	Decrease $\geq 50\%$ (from screening)	Increase $\geq 50\%$ (from nadir)	Change of -49% to +49%
B	Platelet count	$\geq 100 \times 10^9/L$	$\geq 100 \times 10^9/L$ or increase $\geq 50\%$ over screening	Decrease $\geq 50\%$ (from screening secondary to CLL)	Change of -49% to +49%
	Hemoglobin	$\geq 11.0$ g/dL (untransfused and without erythropoietin)	$\geq 11.0$ g/dL or increase $\geq 50\%$ over screening	Decrease $\geq 2$ g/dL (from screening secondary to CLL)	Increase $< 11$ g/dL or $< 50\%$ over screening or decrease $< 2$ g/dL
	Marrow	Normocellular, no CLL cells, no B-lymphoid nodules	Presence of CLL cells, or of B-lymphoid nodules or not done	Increase of CLL cells by $\geq 50\%$ on successive biopsies	No change in marrow infiltrate
	Neutrophils	$\geq 1.5 \times 10^9/L$ (no exogenous growth factors)	Non-CR (Not meeting criteria for CR)	Non-CR (Not meeting criteria for CR)	Non-CR (Not meeting criteria for CR)
Abbreviations: CLL=chronic lymphocytic leukemia; CR=complete response; PD=progressive disease; PR=partial response; SD=stable disease.					

## **10.9.2 Application of the Lugano Classification for Treatment Response Assessment**

### **10.9.2.1 Overview**

This appendix describes the process for assessing treatment response according to the Lugano Classification [Cheson, B. D., et al 2014] for malignant lymphoma (“Lugano” from now on). This assessment includes anatomic imaging with CT or MRI (size assessments of lymph nodes, extranodal lesions, spleen, and liver), metabolic imaging (whole body assessment with FDG-PET), and clinical findings (physical examination and bone marrow biopsy results), when these are available and appropriate.

Anatomic imaging may include CT, MRI, or some combination of the 2. CT is the most common modality used, and for the purposes of this document the term “CT” will be used to represent all anatomic imaging, no matter which imaging modality is used.

Before treatment (“baseline”), on CT all focal lesions (nodal and extranodal) will be classified as “target” (selected for quantitative assessment) and “non-target” (selected for qualitative assessment). The spleen will be assessed quantitatively (by measuring the vertical length), and the liver will be assessed qualitatively. The FDG-PET will be assessed using the 5-point scale (a method similar to the older Deauville criteria). If bone marrow biopsy is performed, or if there are any physical examination findings that cannot be evaluated by imaging, these should be documented.

After therapy has begun, response assessment will include anatomic response based on CT (when a CT is available), which includes target, non-target, and new focal lesions, as well as spleen and liver size assessment. Metabolic response, when an FDG-PET is available, will be based on the 5-point scale along with qualitative assessment of changes in FDG uptake from preceding timepoints. Anatomic response, metabolic response, and clinical information will be combined to produce the overall response for each timepoint. The criteria are summarized in the table below, and detailed in the following sections.

### **10.9.2.2 Lugano Summary Table**

The following tables summarize the assessments based on both CT and PET, as described in the summary table in the original publication [Cheson, B. D., et al 2014]. For details about implementation, please see the sections following the tables.

### **Complete Response**

Complete Response	PET-Based Response – CMR	CT/MRI-Based Response – CR
Target lesions	Score 1, 2, or 3	Target nodes/nodal masses regress to <1.5 cm in LDi; no extranodal sites of disease remain
Non-target lesions	Not applicable	Absent
Organ enlargement	Not applicable	Regress to normal
New lesions	None	None
Bone marrow	No evidence of FDG-avid disease in marrow	Normal by morphology; if indeterminate, negative by immunohistochemistry
Abbreviations: CMR=complete metabolic response; CR=complete response; CT=computed tomography; FDG=2 fluorodeoxyglucose; LDi=longest diameter; MRI=magnetic resonance imaging; PET=positron emission tomography.		

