### **Progressive Disease**

Progressive disease	PET-Based Response – PMD	CT/MRI-Based Response – PD
Target lesions	Score 4 or 5 with an increase in overall uptake (extent and/or intensity) compared within nadir	Growth of any target lesion: Increase $\geq 50\%$ from nadir PPD and Increase in LD i or SD i from nadir of: $\geq 0.5$ cm for lesions $< 2$ cm $\geq 1.0$ cm for lesions $\geq 2$ cm and Current LD i $> 1.5$ cm for a lymph node or $\geq 1.0$ cm for an extranodal lesion
Non-target lesions	Not applicable	Clear progression of pre-existing non-target lesions
New lesions	New FDG-avid foci consistent with lymphoma rather than another cause (eg, infection, inflammation). If uncertain regarding cause of new lesions, biopsy or interval scan may be considered.	Regrowth of previously resolved lesions A new node $> 1.5$ cm in LD i A new extranodal site of any size so long as its presence is unequivocal and attributable to lymphoma
Organ enlargement	Not applicable	When splenomegaly was already present, the excess length must increase by $\geq 50\%$ ( $\geq 1$ cm absolute increase) from nadir. If no prior splenomegaly, or prior splenomegaly had resolved, spleen length must increase by $\geq 2$ cm to $> 13$ cm.
Bone marrow	New or recurrent FDG-avid foci, confirmed by biopsy	New or recurrent involvement
Abbreviations: CT=computed tomography; FDG=2 fluorodeoxyglucose; LD i =longest diameter; MRI=magnetic resonance imaging; PET=positron emission tomography; PD=progressive disease; PMD=progressive metabolic disease; PPD=product of perpendicular diameters; SD i =short axis diameter.		

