## **10.9.2.3.2 Post-baseline Assessment**

### **Target lesions**

At every timepoint after screening, each target lesion is measured. Calculate the PPD for each target lesion and the SPD for all target lesions together. Response categories are as defined below:

- Complete Response (CR): All target lymph nodes must have regressed to normal size defined as  $\leq 1.5$  cm in LDi. Target extranodal sites must be absent (0 by 0 cm).
- Partial Response (PR):  $\geq 50\%$  decrease in SPD of target lesions from baseline, and no individual lesion meets the criteria for progression.
- Progressive Disease (PD): Target lesion progression is based on the progression of any single lesion (not a change in the SPD), which meets all of the following requirements:
  - The lesion must have increased by  $\geq 50\%$  from its nadir in PPD.
  - For a lymph node, it must be  $> 1.5$  cm in LDi, and for an extranodal lesion it must be  $\geq 1.0$  cm in LDi.

- And one of the following:
  - o For lesions <2 cm at nadir, the lesion's LDi or SDi must have increased by  $\geq 0.5$  cm at the current timepoint from its nadir.
  - o For lesions  $\geq 2$  cm at nadir, the lesion's LDi or SDi must have increased by  $\geq 1$  cm at the current timepoint from its nadir.
- Stable Disease (SD): A target lesion assessment of SD requires all of the following:
  - Target lesions do not meet the criteria for CR or PR
  - No individual lesion meets the criteria for progression
- Not Evaluable (NE): When a target lesion identified at baseline cannot be evaluated at a post-baseline timepoint due to missing imaging, poor image quality, changes in the lesion or background that precludes assessment, or focal therapy or other procedures that change the lesion size, the target lesion assessment will be NE, unless progression is assessed in another target lesion.

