### **Spleen response**

The spleen will be measured in the craniocaudal length as at baseline, and the enlarged portion calculated by subtracting 13 cm. Response categories for the spleen are as defined below:

- Normal (CR): Spleen was enlarged at baseline and has regressed to  $\leq 13$  cm at the current timepoint or the spleen was assessed as normal at baseline and is still normal, or there is radiological evidence of splenectomy at baseline.
- Partial Resolution (PR): Spleen was assessed as enlarged at baseline, and its excess length has decreased by  $\geq 50\%$ .
- Stable Splenomegaly (SD): No decrease consistent with PR and no increase consistent with progression

- Unequivocal increase (PD): The spleen is assessed as PD if any of the following are true:
  - Recurrent splenomegaly: A spleen which was abnormal at baseline (>13 cm) first returned to normal, but at the current timepoint the spleen increases by >2 cm from its nadir and the length is >13 cm.
  - New splenomegaly: No prior splenomegaly and spleen increases by >2 cm from baseline and the length is >13 cm.
  - Progression of existing splenomegaly: A spleen which is abnormal at baseline has the enlarged portion increase by  $\geq 50\%$ , and by  $\geq 1$  cm in absolute measurement, at the current timepoint from its nadir value.

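### Appendix 9 gives two normal-node cut-offs for CR in both Lugano and iwCLL, and two Lugano spleen progression thresholds; few participants are likely to be affected

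*Combined protocol and SAP*

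**What the plan says.** **Lugano nodes.** For CT-based CR the summary table in 10.9.2.2 asks for: "Target nodes/nodal masses regress to <1.5 cm in LDi; no extranodal sites of disease remain". The detailed target-lesion rule in 10.9.2.3.2 has "normal size defined as $\leq 1.5$ cm in LDi", that is, 1.5 cm or less.

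**iwCLL nodes.** The target-lesion rule in 10.9.1.2.2 uses the same inclusive wording, "normal size defined as $\leq 1.5$ cm in LDi". The overall CR definition in 10.9.1.3 lists under Group A "All lymph nodes (none $\geq 1.5$ cm", so it excludes a 1.5 cm node. The summary table in 10.9.1.4 gives no size; its entry is "CR (see lymph node response table". The lymph node response table it points to gives no size either.

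**Lugano spleen.** The Progressive Disease table in 10.9.2.2 reads "If no prior splenomegaly, or prior splenomegaly had resolved, spleen length must increase by" and continues with 2 cm or more, to above 13 cm. The spleen text in 10.9.2.3.2 requires, for recurrent splenomegaly, that "the spleen increases by >2 cm from its nadir and the length is >13 cm", and uses the same strict sign for new splenomegaly. At baseline (10.9.2.3.1) a spleen is normal below 13 cm and enlarged above 13 cm. After baseline (10.9.2.3.2) 13 cm or less counts as normal.

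**The concern.** These are working thresholds for the investigator's response and progression calls. Diameters and spleen lengths are rounded readings, so a value that falls exactly on the boundary can occur. Two sites reading different pages of the same appendix could then classify identical scans differently.

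Three things depend on the call:

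- ORR, a secondary endpoint, if the change crosses the line between response and no response.
- DOR, also secondary, if the change decides whether a visit counts as progression.
- In CLL/SLL, who has marrow and MRD sampling, because both follow from CR (Section 1.3.1 and Section 8.2.1.1).

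**Working it through.** The plan states no figure here to reproduce, so the first step is to compare the rules.

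**1. A node recorded at exactly 1.5 cm LDi**

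| Criteria | Place | Rule for CR | Result |
|---|---|---|---|
| Lugano | 10.9.2.2, summary table | below 1.5 cm | not CR |
| Lugano | 10.9.2.3.2, target lesions | 1.5 cm or less | CR |
| iwCLL | 10.9.1.2.2, target lesions | 1.5 cm or less | target CR |
| iwCLL | 10.9.1.3, CR definition | no node of 1.5 cm or more | not overall CR |

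The neighbouring rules use above 1.5 cm: measurable nodes in 10.9.1.2.1 and 10.9.2.3.1, and new nodes in 10.9.1.2.2 and 10.9.2.3.2. They fit the inclusive cut-off.

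**2. Lugano anatomic call under the strict rule**

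If CR is not met, PR needs an SPD fall of at least 50%; otherwise the call is SD. For a single target node, fall = 1 − (follow-up LDi × SDi)/(baseline LDi × SDi). The node sizes below are illustrative assumptions.

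| Baseline (cm) | Follow-up (cm) | Fall | 1.5 cm or less | Below 1.5 cm |
|---|---|---|---|---|
| 1.6 × 1.2 | 1.5 × 1.1 | 1 − 1.65/1.92 = 14.1% | CR | SD |
| 2.0 × 1.5 | 1.5 × 1.1 | 1 − 1.65/3.00 = 45.0% | CR | SD |
| 2.2 × 1.6 | 1.5 × 1.1 | 1 − 1.65/3.52 = 53.1% | CR | PR |
| 3.0 × 2.0 | 1.5 × 1.0 | 1 − 1.50/6.00 = 75.0% | CR | PR |

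If the node keeps its shape, the fall is 1 − (1.5/L)² for baseline LDi L. It reaches 50% at L = 1.5 × √2 = 2.12 cm. The SD result therefore needs a baseline LDi above 1.5 cm (to be measurable) and below about 2.1 cm.

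**3. What that does to ORR**

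CR and PR are both objective responses, so CR against PR changes neither ORR nor the date of first response. CR against SD can move one participant. Illustration with exact 95% intervals:

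- n = 6: 1/6 = 16.7% (0.4 to 64.1) against 2/6 = 33.3% (4.3 to 77.7).
- n = 12: 1/12 = 8.3% (0.2 to 38.5) against 2/12 = 16.7% (2.1 to 48.4).

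**4. iwCLL**

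Under 10.9.1.2.2 the 1.5 cm node is target CR. With non-target CR and no new lesions, the lymph node response table returns CR, and 10.9.1.4 carries that forward. A reader of 10.9.1.3 must refuse overall CR. What replaces it depends on the PR rule in 10.9.1.3: how many Group A and Group B parameters were abnormal and have improved.

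**5. Lugano spleen**

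Take a spleen with no prior enlargement that goes from 11.5 to 13.5 cm (illustrative): 13.5 − 11.5 = 2.0 cm, ending above 13 cm. The table calls this PD; the text does not. The anatomic response table in 10.9.2.3.2 makes spleen PD an anatomic PD, and the table in 10.9.2.5 makes anatomic PD an overall PD for any metabolic response.

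A spleen of 13.0 cm at baseline has no category, and the category decides which growth rule applies. Its excess length is 13.0 − 13 = 0, so any growth satisfies the 50% condition. If treated as enlarged, a rise of 1 cm would be PD; if treated as normal, the 2 cm rule applies.

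**The case against.** **The Lugano tables defer to the text.** Sections 10.9.2.1 and 10.9.2.2 describe the tables as summaries and send readers to the following sections for implementation. That makes the text the natural choice, but it is a pointer and not a stated order of precedence. It also does not cover iwCLL, where the stricter rule is the overall CR definition itself.

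**PET decides most Lugano calls.** This stands for the node cut-off. Under 10.9.2.5 a complete metabolic response with anatomic CR, PR or SD, negative marrow and no lesions on examination is overall CR, and an earlier PET may be carried forward. Section 1.3.1 requires PET in FDG-avid disease at baseline, at Weeks 12 and 24 and to confirm CR. The node conflict is therefore largely confined to non-FDG-avid disease and CT-only assessments. The argument does not help with the spleen, because anatomic PD overrides PET.

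**Progression may be confirmed first.** Section 8.2.2.1.1 lets the investigator keep a clinically stable participant on treatment until repeat imaging at 4 to 6 weeks. That softens the spleen conflict but does not say which threshold the repeat scan must meet.

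Three stronger readings are tempting, and the documents support none of them:

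- That text and tables conflict in both criteria sets. This is true of Lugano only; in iwCLL both statements are text and the tables carry no size.
- That a 1.5 cm node can drop a CLL/SLL participant straight from CR to SD because SPD fell by less than 50%. The target-lesion rule still gives nodal CR, and overall PR depends on the other parameters.
- That a sizeable share of participants would be misclassified. The documents give no distribution of node sizes or shrinkage, so any such percentage would rest on invented inputs.

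**Conclusion.** The inconsistency is real but minor. Appendix 9 states the nodal CR cut-off two ways in Lugano and two ways in iwCLL, and gives two signs for the 2 cm Lugano spleen increase. It also leaves a 13.0 cm baseline spleen unclassified.

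The node conflict changes ORR in Lugano only for a CT-determined call with an SPD fall under 50%. The limit of about 2.1 cm baseline LDi assumes one target node of unchanged shape. In iwCLL the conflict governs overall CR and the sampling that follows from it. The spleen conflict can change a progression call, and so DOR, whatever the PET shows.

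Few participants are likely to be affected. The study enrols about 6 to 12. Section 2.2.2.3 reports 2 complete remissions among 57 CLL/SLL participants at 65 mg in BELLWAVE-001. In BELLWAVE-003 the 9 responders among 23 are fully accounted for by 6 PR and 3 PRL, so there was no CR. If all 12 participants had CLL/SLL and the first rate applied, 12 × 2/57 = 0.42 CRs would be expected, and only those with a node at exactly 1.5 cm would be in question. That figure is a rough guide and says nothing about Lugano participants.

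**What to change.** - Within each criteria set, use one nodal cut-off for CR: reconcile 10.9.1.2.2 with 10.9.1.3 for iwCLL, and the Complete Response table in 10.9.2.2 with 10.9.2.3.2 for Lugano. The inclusive version, 1.5 cm or less, agrees with the appendix's own measurability and new-node rules. Check it against the cited iwCLL and Lugano criteria before adopting it, since the endpoints are defined by those criteria.
- Reconcile the spleen increase in the Progressive Disease table of 10.9.2.2 with the spleen text in 10.9.2.3.2, and the baseline definition in 10.9.2.3.1 with the post-baseline definition in 10.9.2.3.2, so that each threshold is stated once. A progression call also governs stopping of treatment, so the choice belongs to the sponsor and is not proposed here.
- State in 10.9.2.2 whether the table or the detailed text prevails if they differ.

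The cost is a few symbol-level edits and one sentence in Appendix 9. No new data or assessments are needed. For scans already read, a listing of values exactly on these boundaries would show whether any call needs a second look.
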